AUC_{last} Area under the concentration – time curve from time zero to time of last measurable

concentration

AUC_{tau} Area under the concentration – time curve between consecutive dosing

CA Competent authority (also CCMO)
CHDR Centre for Human Drug Research

CI Confidence Interval CV Coefficient of variation

EC Ethics Committee (also Medical Research Ethics Committee (MREC); in Dutch:

Medisch Ethische Toetsing Commissie (METC).

ECG Electrocardiogram
GCP Good Clinical Practice

ICH International Conference on Harmonization

Max Maximum

MedDRA Medical Dictionary for Regulatory Activities

min Minutes Min Minimum

SAE Serious Adverse Event SD Standard Deviation

SEM Standard Error of the Mean

SOC System Organ Class

SOP Standard Operating Procedure

SUSAR Suspected Unexpected Serious Adverse Reaction

t_{1/2} Terminal Elimination Half-life

WMO Medical Research Involving Human Subjects Act; in Dutch: Wet Medisch-

wetenschappelijk Onderzoek met Mensen.

PROTOCOL SYNOPSIS

Title

Methodological trial to investigate the dose-response relationship, test-retest reliability, and tolerance to repeated exposure of the 35% carbon dioxide experimental panic challenge in CO2-sensitive healthy volunteers.

Short Title

Methodological optimization of the CO2 challenge

Principal investigator & Trial Site

[name], Centre for Human Drug Research, [name], The Netherlands

Background & Rationale

Panic attacks (PAs) are human fear-related phenomena characterized by episodic feelings of dread and discomfort, cognitive misinterpretation of potential threat and physical symptoms related to autonomic nervous system (ANS) activation. Since PAs usually occur without warning, they are not amenable to real-time assessment, and as a result, are assessed retrospectively by structurally administering patient and clinician-rated psychometric questionnaires in a research setting. The validity of such methodologies is obviously questionable and creates the urgent need for alternative methodologies to investigate PAs in health and disease and to establish efficacy of anxiolytic drugs.

In the past, different methodologies have been utilized to characterize PAs in humans. Fear challenges with for instance compounds such as lactate, yohimbine and cholecystokinin tetrapeptide (CCK-4) or self-induced hyperventilation yielded inconsistent results and has led to their abandonment in recent years. Currently, the acute intrapulmonary administration of carbon dioxide (CO2) is widely considered a reliable challenge model to experimentally provoke a panic reaction that phenomenologically and physiologically resembles PAs. Acute CO2 inhalation therefore experimentally induces a panic reaction in humans that displays adequate face-validity as a panic challenge in experimental research.

The CO2 inhalation model for panic has undergone both technical innovation and relatively extensive validation since the 1980's. Panic disorder (PD) patients consistently display the highest sensitivity to CO2, followed by first degree relatives of PD patients and healthy volunteers, which show a concentration dependent sensitivity to inhaled CO2. Additionally, registered anxiolytic drugs administered in clinically effective therapeutic doses reduce CO2 sensitivity in healthy volunteers and patients over time.

In the past, various CO2 regimens have been applied to induce PAs in human populations. Although both single and double vital capacity inhalations of 35% CO2/65% O2 consistently demonstrate panicogenic effects in healthy volunteers and PD patients or their first-degree relatives, the CO2 sensitivity of both similar patient and healthy groups tend to vary between research groups. Since varying CO2 administration protocols which include both single and double vital capacity administrations are being applied across research groups, differences in CO2 sensitivity could very well be the result of unintended methodological variability. The lack of a standardized procedure to test sensitivity to CO2 therefore hampers accurate comparisons between tests performed under different protocols. A better understanding of whether a single or double breath 35% CO2/65% O2 is sufficient to induce PAs is expected to contribute to the validity of acute CO2 inhalation as tool in pathophysiological research and in early CNS drug development.

The differential response to single versus double 35% CO2 vital capacity inhalation of CO2 remains to be examined systematically to further validate it as experimental paradigm for future use. To the best of our knowledge no study has been previously published that compares single and double vital capacity 35% CO2 inhalation in a single study. Therefore, we aim to investigate the panicogenic effects of a single vs. a double vital capacity method 35% CO2 in healthy volunteers. We hypothesize that 35% CO2 double vital capacity inhalation is associated with a higher percentage of subjects experiencing a panic attack compared to single vital capacity inhalation.

Additionally, this study also seeks to systematically investigate the test-retest reliability of the CO2 inhalation challenge in healthy volunteers who are sensitive to the anxiogenic effects of CO2 inhalation. Previous research has only examined intervals of up to a few weeks, leaving it unclear whether individuals who are sensitive to the 35% CO2 inhalation challenge remain sensitive for longer periods, possibly years later. Leibold et al. (2015¹) found that a single vital capacity breath of 35% CO2 inhalation demonstrated good reliability of subjective fear in PD patients, but only used an interval of one week between inhalations. These previous studies were conducted in patients with PD, who exhibit greater sensitivity to the anxiogenic effects of the CO2 challenge compared to healthy volunteers. By analysing this effect in a different population, this study also aims to provide a more comprehensive understanding of the test-retest reliability of the CO2 inhalation challenge.

Finally, this study seeks to investigate whether tolerance or desensitization occurs in healthy volunteers who were previously sensitive to the CO2 challenge. While past research has explored this topic in patients with panic disorders, studies in healthy volunteers who were screened for sensitivity to the anxiogenic effects of CO2 challenges are non-existent. Previous tolerance studies have been conducted in healthy volunteers, but these participants were not selected based on their sensitivity to the anxiogenic effects of CO2 inhalation. If tolerance does not occur after four challenges administered one week apart over the course of a month, this would justify conducting future three-way crossover studies.

Objective(s) and endpoints

Primary objectives	Endpoints
To investigate the difference in panic response (i.e., "dose-response") between single and double vital capacity 35% CO ₂ /65% O ₂ inhalation in CO ₂ -sensitive healthy volunteers.	The difference in the occurrence and severity of a panic attack between the single and double vital capacity 35% CO ₂ /65% O ₂ inhalation as measured by the difference in pre- and post CO ₂ challenge questionnaires Panic Symptoms List-IV (PSL-IV), VAS subjective fear, and VAS discomfort.
To investigate the test-retest reliability of repeated double vital capacity 35% CO2/65% O2 inhalation in CO2-sensitive healthy volunteers.	The difference in the occurrence and severity of a panic attack between the test-retest double vital capacity 35% CO ₂ /65% O ₂ inhalation as measured by the difference in pre- and post CO ₂ challenge questionnaires Panic Symptoms List-IV (PSL-IV) and VAS subjective fear, and VAS discomfort.
To investigate whether repeated double vital capacity 35% CO2/65% O2 inhalation leads to tolerance/desensitization in CO2-sensitive healthy volunteers.	The difference in the occurrence and severity of a panic attack in the repeated 35% CO ₂ /65% O ₂ inhalation as measured by the difference in pre- and post CO ₂ challenge questionnaires Panic Symptoms List-IV (PSL-IV), VAS subjective fear, and VAS discomfort.
To establish whether CO2 sensitivity represents a stable trait phenomenon in CO2-sensitive healthy volunteers.	The difference in the occurrence and severity of a panic attack in the repeated 35% CO ₂ /65% O ₂ inhalation as measured by the difference in pre- and post CO ₂ challenge questionnaires Panic Symptoms List-IV (PSL-IV), VAS subjective fear, and VAS discomfort.
Secondary objectives	Endpoints
Explore the effects of single and (repeated) double breath 35% CO ₂ /65% O ₂ on heart rate and blood pressure in CO ₂ -sensitive healthy volunteers.	Difference in mean change from pre-CO2 to post-CO2 challenge in vital sign measurements (systolic blood pressure, diastolic blood pressure, heart rate).

Explore the effects of single and (repeated) double breath 35% CO2/65% O2 on neuro-endocrine mediated autonomic nervous system activation and orexin/hypocretin release in CO2-sensitive healthy volunteers.	Differences in plasma ACTH, prolactin, orexin-1 and cortisol, and saliva amylase and cortisol from pre-CO2 to post-CO2 challenge.
To explore the relationship between baseline personality and temperament characteristics and individual response to CO2 in CO2-sensitive healthy volunteers.	Dutch Personality Questionnaire (DPQ), Cloninger Temperament Character Inventory (TCI), and Spielberger State-Trait Anxiety Inventory (STAI)

Design

Five visit trial to investigate the dose-response relationship, test-retest reliability, and tolerance to repeated exposure of the 35% carbon dioxide experimental panic challenge in 20 CO2-sensitive healthy volunteers.

[figure not shown]
Out of the five scheduled visits (Figure 1):

- single or a double vital capacity inhalation of 35% CO2/65% O2 will be randomized over a 2-way cross-over part consisting of visit 1 and visit 2. During the first visit, half of the participants (n=10) will be randomized to receive a single vital capacity inhalation of CO2 while the other half (n=10) will be randomized to double vital capacity inhalation of CO2. Approximately a week later, the groups will switch, with the group originally assigned the single vital capacity inhalation now receiving the double vital capacity inhalation, and vice versa.
- visits 3, 4 and 5 will follow a fixed pattern, with all participants receiving only double vital capacity 35% CO2/65% O2 inhalation roughly a week apart.

On the first day, prior to the CO2 challenge, the Spielberger State-Trait Anxiety Inventory (STAI), Dutch Personality Questionnaire (DPQ), and Cloninger Temperament Character Inventory (TCI) will be administered according to the schedule of assessments (Table 1).

To evaluate the severity of panic symptoms, each subject will complete the PSL-IV, VAS Fear and VAS Discomfort within five minutes before and as soon as possible (but no later than 15 minutes) after the CO2 challenge according to the schedule of assessments (Table 1). In addition, the STAI Y1 will be administered within 20 minutes before and as soon as possible after the CO2 challenge. Throughout the procedure, vital signs such as blood pressure and heart rate will be continuously monitored. Lastly, biomarkers for neuroendocrine autonomic nervous system activation (plasma ACTH, cortisol, and prolactin; saliva alpha-amylase and cortisol) and plasma orexin-1 will be assessed according to the schedule of assessments (Table 1).

Figure 1: Schematic overview of design.

Investigational drug

Not applicable.

Subjects / Groups

A total of 20 healthy subjects, who previously have shown to be sensitive to the panicogenic effects of the CO2 challenge, of either gender will be enrolled into the study following satisfactory completion of a screening (ECG and medical history) where eligibility for the study will be checked.

Inclusion criteria

- 1. Healthy male or female aged between 18 and 65 years (inclusive) at screening who have been demonstrated to be sensitive to the panicogenic effects of the CO2 challenge in previous studies.
- 2. Sensitivity to the fear-inducing effects of 35% CO2 double-breath inhalation is defined as an increase from pre-CO2 to post-CO2 challenge in the following: PSL-IV total scores ≥4 with at least 1-point increase for at least 4 of the symptoms specified in the PSL-IV and an increase on the Visual Analog Scale (VAS) Fear of at least 25 mm.
- 3. BMI of 18-32 kg/m₂ (inclusive).
- 4. Non-smoker for at least 3 months.

Exclusion criteria

- 1. Subjects with a clinically significant current or past personal or family history of any psychiatric disorder as classified by DSM-4 or DSM-5 criteria.
- 2. Current or past history of alcohol or any substance abuse or dependence disorder within the past 12 months.
- 3. Clinically significant ECG abnormalities.
- 4. Clinically significant abnormality of the lungs (e.g., COPD, asthma, lung fibrosis) and hematologic diseases concerning hemoglobin (e.g., thalassemia and sickle cell disease).
- 5. Important cardiovascular history, or suspicion of infarct, cardiomyopathy, cardiac failure, TIA, angina pectoris, cardiac arrhythmias, CVA.
- 6. Personal or familial history of cerebral aneurysm.

Concomitant medications

Certain concomitant medications are allowed, only after the rationale is clearly documented by the investigator.

Tolerability / safety endpoints

(Serious) adverse events ((S)AEs) will be collected throughout the study at every study visit. ECG will be obtained during the first visit of the study according to the Visit and Assessment Schedule

Sample Size Justification

This is a methodological study; therefore, the sample size is not based on statistical considerations. We've chosen a sample size of 20 participants because our current database includes 180 individuals sensitive to the panic-inducing effects of the CO2 challenge. Based on our previous experiences, selecting 20 participants from this group for the study is realistic

Statistical methodology

- d. The PSL-IV, VAS Fear, and VAS Discomfort will be completed by the subject within 5 minutes before and as soon as possible, but within 15 minutes, after the CO2 Challenge.

CHDR2344

- e. During each visit, ACTH, prolactin, cortisol, and orexin-1 in blood plasma will be collected at specific timepoints surrounding the CO2 challenge: one will be taken 15 minutes before the challenge, another within the 5-minute window immediately preceding the challenge, a third one directly within the 5-minutes following the challenge, and the remaining at 15-, 30-, 60-, and 120-minutes intervals post-challenge.
- f. During each visit, cortisol and amylase in saliva will be collected at specific timepoints surrounding the CO2 challenge: one will be taken 10 minutes before the challenge, another within 1-minute window immediately preceding the challenge, a third one directly within the 1-minutes following the challenge, and the remaining at 10-, 20-, 40-, and 60-minutes intervals post-challenge

1 BACKGROUND AND RATIONALE

1.1 Context

Panic attacks (PAs) are human fear-related phenomena characterized by episodic feelings of dread and discomfort, cognitive misinterpretation of potential threat and physical symptoms related to autonomic nervous system (ANS) activation. Since PAs usually occur without warning, they are not amenable to real-time assessment, and as a result, are assessed retrospectively by structurally administering patient and clinician-rated psychometric questionnaires in a research setting. The validity of such methodologies is obviously questionable and creates the urgent need for alternative methodologies to investigate PAs in health and disease and to establish efficacy of anxiolytic drugs.

In the past, different methodologies have been utilized to characterize PAs in humans. Fear challenges with for instance compounds such as lactate, yohimbine and cholecystokinin tetrapeptide (CCK-4) or self-induced hyperventilation yielded inconsistent results and has led to their abandonment in recent years. Currently, the acute intrapulmonary administration of carbon dioxide (CO2) is widely considered a reliable challenge model to experimentally provoke a panic reaction that phenomenologically and physiologically resembles PAs. Acute CO2 inhalation therefore experimentally induces a panic reaction in humans that displays adequate face-validity as a panic challenge in experimental research.

The CO2 inhalation model for panic has undergone both technical innovation and relatively extensive validation since the 1980's. Panic disorder (PD) patients consistently display the highest sensitivity to CO2, followed by first degree relatives of PD patients and healthy volunteers, which show a concentration dependent sensitivity to inhaled CO2. Additionally, registered anxiolytic drugs administered in clinically effective therapeutic doses reduce CO2 sensitivity in healthy volunteers and patients over time.

In the past, various CO2 regimens have been applied to induce PAs in human populations. Although both single and double vital capacity inhalations of 35% CO2/65% O2 consistently demonstrate panicogenic effects in healthy volunteers and PD patients or their first-degree relatives, the CO2 sensitivity of both similar patient and healthy groups tend to vary between research groups. Since varying CO2 administration protocols which include both single and double vital capacity administrations are being applied across research groups, differences in CO2 sensitivity could very well be the result of unintended methodological variability. The lack of a standardized procedure to test sensitivity to CO2 therefore hampers accurate comparisons between tests performed under different protocols. A better understanding of whether a single or double breath 35% CO2/65% O2 is sufficient to induce PAs is expected to contribute to the validity of acute CO2 inhalation as tool in pathophysiological research and in early CNS drug development.

The differential response to single versus double 35% CO2 vital capacity inhalation of CO2 remains to be examined systematically to further validate it as experimental paradigm for future use. To the best of our knowledge no study has been previously published that compares single and double vital capacity 35% CO2 inhalation in a single study. Therefore, we aim to investigate the panicogenic effects of a single vs. a double vital capacity method 35% CO2 in healthy volunteers. We hypothesize that 35% CO2 double vital capacity inhalation is associated with a higher percentage of subjects experiencing a panic attack compared to single vital capacity inhalation.

Additionally, this study also seeks to systematically investigate the test-retest reliability of the CO2 inhalation challenge in healthy volunteers who are sensitive to the anxiogenic effects of CO2 inhalation. Previous research has only examined intervals of up to a few weeks, leaving it unclear whether individuals who are sensitive to the 35% CO2 inhalation challenge remain sensitive for longer periods, possibly years later. Leibold et al. (2015¹) found that a single vital capacity breath of 35% CO2 inhalation demonstrated good reliability of subjective fear in PD patients, but only used an interval of one week between inhalations. These previous studies were conducted in patients with PD, who exhibit greater sensitivity to the anxiogenic effects of the CO2 challenge compared to

healthy volunteers. By analysing this effect in a different population, this study also aims to provide a more comprehensive understanding of the test-retest reliability of the CO2 inhalation challenge.

Finally, this study seeks to investigate whether tolerance or desensitization occurs in healthy volunteers who were previously sensitive to the CO2 challenge. While past research has explored this topic in patients with panic disorders, studies in healthy volunteers who were screened for sensitivity to the anxiogenic effects of CO2 challenges are non-existent. Previous tolerance studies have been conducted in healthy volunteers, but these participants were not selected based on their sensitivity to the anxiogenic effects of CO2 inhalation. If tolerance does not occur after four challenges administered one week apart over the course of a month, this would justify conducting future three-way crossover studies.

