1.2.6 Statistical hypotheses and sample size

This is an observational, methodological study; therefore, the sample size is not based on statistical considerations. We've chosen a sample size of 20 participants because our current database includes 180 individuals sensitive to the panic-inducing effects of the CO2 challenge. Based on our previous experiences, selecting 20 participants from this group for the study is realistic.

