2 STUDY OBJECTIVES AND ENDPOINTS

Primary objectives	Endpoints
To investigate the difference in panic response (i.e "dose-response") between single and double vital capacity 35% CO ₂ /65% O ₂ inhalation in CO ₂ -sensitive healthy volunteers. To investigate the test-retest reliability of repeated double vital capacity 35% CO ₂ /65%	The difference in the occurrence and severity of a panic attack between the single and double vital capacity 35% CO ₂ /65% O ₂ inhalation as measured by the Panic Symptoms List-IV (PSL-IV), VAS subjective fear, and VAS discomfort. The difference in the occurrence and severity of a panic attack between the test-retest double
O2 inhalation in CO2-sensitive healthy volunteers.	vital capacity 35% CO ₂ /65% O ₂ inhalation as measured by the Panic Symptoms List-IV (PSL-IV) and VAS subjective fear, and VAS discomfort.
To investigate whether repeated double vital capacity 35% CO2/65% O2 inhalation leads to tolerance/desensitization in CO2-sensitive healthy volunteers.	The difference in the occurrence and severity of a panic attack in the repeated 35% CO ₂ /65% O ₂ inhalation as measured by the Panic Symptoms List-IV (PSL-IV), VAS subjective fear, and VAS discomfort.
To establish whether CO2 sensitivity represents a stable trait phenomenon in CO2-sensitive healthy volunteers.	The difference in the occurrence and severity of a panic attack in the repeated 35% CO ₂ /65% O ₂ inhalation as measured by the Panic Symptoms List-IV (PSL-IV), VAS subjective fear, and VAS discomfort.
Secondary objectives	Endpoints
Explore the effects of single and (repeated) double breath 35% CO ₂ /65% O ₂ on heart rate and blood pressure in CO ₂ -sensitive healthy volunteers.	Difference in mean change from pre-CO2 to post-CO2 challenge in vital sign measurements (systolic blood pressure, diastolic blood pressure, heart rate).
Explore the effects of single and (repeated) double breath 35% CO2/65% O2 on neuro-endocrine mediated autonomic nervous system activation and orexin/hypocretin release in CO2-sensitive healthy volunteers.	Differences in plasma ACTH, prolactin, orexin-1 and cortisol, and saliva amylase and cortisol from pre-CO2 to post-CO2 challenge.
To explore the relationship between baseline personality and temperament characteristics and individual response to CO2 in CO2-sensitive healthy volunteers.	Dutch Personality Questionnaire (DPQ), Cloninger Temperament Character Inventory (TCI), and Spielberger State-Trait Anxiety Inventory (STAI)

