8.3 Power calculation

Not applicable.

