8.9.3 Occurrence of tolerance after repeated exposure

The occurrence and intensity of PAs in CO2 sensitive healthy subjects caused by a double (and single) vital capacity inhalation of 35% CO2/65% O2.

For the occurrence of PAs repeated measures logistic regression will be used with challenge number as fixed factor and subject as random factor.

The intensity of PAs will be analyzed with repeated measures mixed model ANCOVA with challenge number as fixed factor, subject as random factor and baseline as covariate.

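### The protocol attaches a consequence to absence of tolerance but gives no criterion for it, and a null challenge-number test in 20 subjects could not establish it

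*Protocol*

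**What the plan says.** Tolerance is one of the primary objectives in section 2: "To investigate whether repeated double vital capacity 35% CO2/65% O2 inhalation leads to tolerance/desensitization in CO2-sensitive healthy volunteers". Section 1.1, repeated in the synopsis background, attaches a consequence to its absence: if none is seen after four challenges at weekly intervals, "this would justify conducting future three-way crossover studies". Section 1.2.5, item 3, states the goal for the repeated double inhalations as consistency that is itself statistically significant.

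The inferential analysis is in section 8.9.3. For severity, "The intensity of PAs will be analyzed with repeated measures mixed model ANCOVA with challenge number as fixed factor", with subject as random factor and baseline as covariate. For occurrence, "repeated measures logistic regression will be used with challenge number as fixed factor and subject as random factor". Section 8.9 adds descriptive summaries, graphs of means over time and a frequency table of panic attacks.

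On the number of subjects, section 1.2.6 says that "the sample size is not based on statistical considerations" and explains the choice of 20 by the size of the recruitment database. The entry for power in section 8.3 reads "Not applicable". The protocol states no largest acceptable decline, equivalence limit or confidence-interval rule.

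**The concern.** A model with challenge number as a fixed factor asks whether responses differ between challenges. A significant fall would be evidence of tolerance. A non-significant result shows only that a fall was not detected, and the upper confidence limit for the fall may still be large. The goal in section 1.2.5 and the consequence in section 1.1 both need positive evidence of stability. Section 8.9.3 is not set up to give it, and no other part of the protocol says what would count as tolerance not occurring.

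The risk is not remote. Section 1.2.1 itself says that tolerance may develop on repeated exposure in sensitive subjects. If a moderate fall went undetected and the challenge were taken as stable, later drug crossovers would carry an unplanned period effect, and less response would be left for a drug to suppress in later periods.

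**Working it through.** The figure of 20 has no stated statistical inputs, so there is no calculation to reproduce. The check asks what 20 subjects can say about a fall in VAS Fear response (change from pre- to post-challenge) between the first and fourth double challenge.

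**Inputs from the protocol**
- n = 20 (section 1.2.6).
- Four double challenges per subject: one at visit 1 or 2, then visits 3, 4 and 5 (section 3.1). Error degrees of freedom are (20 − 1) × (4 − 1) = 57.
- The only VAS Fear reference size is the 25 mm rise that defines sensitivity at entry (section 4.2). It is a minimum for entry, not a tolerance margin.

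**Assumptions**
- Within-subject SD 10, 15, 20 or 25 mm (none is given).
- Two-sided 5% test (level and sidedness are not given).
- All 20 subjects evaluable.
- True fall of 10 mm, which is 10/25 = 40% of the entry threshold, or 25 mm as a large fall.

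**Step 1: precision and chance of missing a fall.** SE = √2 × SD / √20. At SD 15 mm: 1.414 × 15 / 4.472 = 4.74 mm. The 95% half-width is 2.002 × SE. The chance of a non-significant result comes from the noncentral t with 57 df and noncentrality fall/SE; for 10 mm at SD 15 mm this is 10/4.74 = 2.11, giving 46%.

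| Within-subject SD (mm) | 10 | 15 | 20 | 25 |
|---|---|---|---|---|
| SE (mm) | 3.2 | 4.7 | 6.3 | 7.9 |
| 95% CI half-width (mm) | 6.3 | 9.5 | 12.7 | 15.8 |
| Fall detectable with 80% power (mm) | 9.0 | 13.5 | 18.0 | 22.5 |
| 10 mm fall non-significant | 13% | 46% | 66% | 76% |
| 25 mm fall non-significant | <0.1% | 0.1% | 2.7% | 12.5% |

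**Step 2: other forms of the test.** A paired t-test (19 df) with SD of the difference 20, 25, 30 or 35 mm misses a 10 mm fall in 44, 60, 71 or 77% of trials. The overall 3-df test across four challenges misses a linear decline totalling 10 mm in 54, 70, 78 or 83%. The result does not depend on the choice of test.

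**Step 3: occurrence of panic attacks.** An exact McNemar comparison with n = 20, assuming 0 to 10% of subjects switch in the opposite direction, misses a true 20-point fall in 80 to 83% of trials and a 30-point fall in 42 to 63%.

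**Step 4: what a confidence-bound rule would achieve.** The one-sided 95% bound is the estimated fall plus 1.672 × SE. Take an illustrative largest acceptable fall of 12.5 mm, half the entry threshold; the protocol does not supply this figure.

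| Within-subject SD (mm) | 10 | 15 | 20 | 25 |
|---|---|---|---|---|
| 1.672 × SE (mm) | 5.3 | 7.9 | 10.6 | 13.2 |
| Largest observed fall that passes (mm) | 7.2 | 4.6 | 1.9 | none |
| Chance of passing if there is no true fall | 99% | 83% | 62% | 47% |

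At SD 25 mm, 13.2 exceeds 12.5, so even an observed fall of zero would not pass; a small observed rise would be needed.

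**The case against.** The strongest reply is that the protocol never says a non-significant test means no tolerance. The three-way crossover sentence is background, and the statistics section sets no decision rule. The section 8.9.3 models will also yield estimates and confidence intervals, and the section 8.9 summaries would make a fall visible. Interpretation thresholds are often left to the statistical analysis plan, and a methodological study may choose its size on feasibility. All of that is fair, and it limits what can be said. It does not supply a criterion: the protocol itself states the consequence and the goal of significant consistency, and the only inference it provides is for a difference.

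The size of the problem also rests on assumptions. No SD is given, and the miss rate for 10 mm runs from 13% to 76%. Because 25 mm is a minimum for entry, 10 mm may be less than 40% of the typical response. Large falls would usually be seen. These points stand.

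The contrast is not perfectly clean either. The single-first half reach their first double challenge after a single inhalation in this study; the double-first half do not. A three-way crossover also needs only three challenges, so first versus fourth covers more exposure than that use requires. The first point calls for sequence in the model. The second does not remove the need for a criterion, since section 1.1 itself speaks of four challenges.

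**Conclusion.** The concern holds in a limited form. The protocol ties a consequence to absence of tolerance and seeks statistically significant consistency, but plans only challenge-number models in a sample of unargued size and gives no criterion for absence. At within-subject SDs of 15 mm or more, a null test would often coexist with a true 10 mm fall (46 to 76% of trials); at 10 mm it would do so in 13%. These figures rest on the assumed SDs, the assumed fall, a two-sided 5% test and 20 completers.

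A reader might infer that the protocol makes a formal go decision on non-significance. It does not: the text says only that later studies would be justified. A reader might also infer that 20 subjects are too few for any conclusion on tolerance. That is not supported, since a 25 mm fall would be missed in at most about 13% of trials over the SDs considered. The weakness concerns moderate tolerance and panic-attack occurrence. This should be fixed, but the trial can run without it.

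**What to change.** Keep 20 subjects and the visit schedule.

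- Before any outcome data are seen, name the VAS Fear response (change from pre- to post-challenge) as the measure for this decision, and set the largest acceptable fall from first to fourth double challenge, with reasons.
- Estimate that contrast from the mixed model with sequence (single-first or double-first) included, and show the change by sequence as well, because a sequence main effect alone adjusts level rather than change.
- Conclude no relevant tolerance only if the one-sided 95% confidence bound, which is the matching limit of the 90% interval, excludes a fall of the chosen size. Otherwise report the estimate with its interval as inconclusive.
- Report panic-attack occurrence as an estimated change with its interval, without a claim of stability.
- Reword the synopsis background, section 1.1 and section 1.2.5 (item 3) so that a null test alone does not justify three-way crossovers.

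The cost is agreement on one margin and some wording. Section 9.5.1 already classes analyses other than those described as non-substantial changes. The real downside is that the trial may end without a conclusion on tolerance: with the illustrative 12.5 mm margin and no true fall, at SD 25 mm it would do so slightly more often than not.
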